6.3.1. Adverse Events

A treatment-emergent AE (TEAE) is defined as any event not present before exposure to study vaccine or any event already present that worsens after exposure to study vaccine. [Note: worsening of a pre-existing condition after vaccination will be reported as a new AE.]

Adverse events will also be evaluated by the investigator for the coexistence of MAAE which is defined as an AE that leads to an unscheduled visit to a healthcare practitioner.

Unsolicited AEs will be coded by PT and SOC using MedDRA and summarized by age cohort, vaccination group, and stage (28 days after any vaccination stage for Part A and Part B separately, and Day1 to End of Study; see [Section 6.1](#) for definitions of vaccination group and stage).

All summary tables (except for the overall summary of AEs) for unsolicited AEs will be presented by SOC and PT for TEAEs with counts of subjects included. SOC will be displayed in internationally agreed order. PT will be displayed in descending order of frequency of total mRNA-1273 and then alphabetically within SOC. When summarizing the number and percentage of subjects with an event, subjects with multiple occurrences of the same AE or a continuing AE will be counted once. Subjects will be presented

according to the highest severity (the strongest relationship) in the summaries by severity (of related AEs), if subjects reported multiple events under the same SOC and/or PT.

Percentages will be based upon the number of subjects in the Safety Set within each vaccination group.

6.3.1.1. Incidence of Adverse Events

An overall summary of unsolicited TEAEs including the number and percentage of subjects who experience the following will be presented:

- Any unsolicited TEAEs
- Any serious TEAEs
- Any unsolicited TEAEs that are medically-attended
- Any unsolicited TEAEs leading to discontinuation from study vaccine
- Any unsolicited TEAEs leading to discontinuation from participation in the study
- Any unsolicited Severe TEAEs
- Any unsolicited TEAEs that are fatal

The table will also include number and percentage of subjects with unsolicited TEAEs that are treatment-related in each of the above categories.

In addition, separate listings containing individual subject adverse event data for unsolicited AEs, unsolicited TEAEs leading to discontinuation from study vaccine, unsolicited TEAEs leading to discontinuation from participation in the study, serious AEs, and unsolicited medically-attended AEs will be provided separately.

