3.4.8 Safety Definitions

3.4.8.1 Adverse Event

An AE is defined as any untoward medical occurrence associated with the use of a drug in humans, whether or not considered drug related.

A treatment-emergent AE (TEAE) is defined as any event not present before exposure to vaccine or any event already present that worsens in intensity or frequency after exposure.

Events Meeting the Adverse Event Definition

- Any abnormal laboratory test result (hematology, clinical chemistry, or PT/PTT) or other safety assessment (eg, electrocardiogram, radiological scan, vital sign measurement), including one that worsens from baseline and is considered clinically significant in the medical and scientific judgment of the investigator.
- Exacerbation of a chronic or intermittent pre-existing condition including either an increase in frequency and/or intensity of the condition.
- New conditions detected or diagnosed after mRNA-1273 vaccine administration even though it may have been present before the start of the study.

Events NOT Meeting the Adverse Event Definition

- Medical or surgical procedure (eg, endoscopy, appendectomy): the condition that leads to the procedure is the AE.
- Situations in which an untoward medical occurrence did not occur (social and/or convenience admission to a hospital).

An AR is any AE for which there is a reasonable possibility that the investigational product caused the AE ([Section 3.4.8.4](#)). For the purposes of investigational new drug safety reporting,

“reasonable possibility” means that there is evidence to suggest a causal relationship between the investigational product and the AE.

An unsolicited AE is any AE reported by the participant that is not specified as a solicited AR in the protocol or is specified as a solicited AR in the protocol but starts outside the protocol-defined post-injection period for reporting solicited ARs (ie, for the 7 days after each injection).

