* Grading for rash and Grade 4 events per Investigator assessment (with exception of fever).

Sources: Guidance for Industry – Toxicity Grading Scale for Healthy Adult and Adolescent Volunteers Enrolled in Preventive Vaccine Clinical Trials; tables for clinical abnormalities (DHHS 2007). Division of AIDS Grading the Severity of Adult and Pediatric Adverse Events (DHHS 2014).

In case of any rash episode observed within 7 days after study injection, the participant will be instructed to contact the study site within 24 hours. During participant evaluation, the investigator should categorize the rash as one of the following:

- Rash no longer present and history not consistent with urticaria.
- Rash no longer present but history is consistent with urticaria.
- Rash present but clinical findings are not consistent with urticaria. Alternative diagnosis should be specified as an AE.
- Rash present and clinical findings consistent with urticaria.

Any solicited AR that meets any of the following criteria must be entered into the participant's source document and must also be recorded as an AE in the participant's Adverse Event eCRF:

- Solicited local or systemic AR that results in a visit to an HCP (MAAE)
- Solicited local or systemic AR leading to the participant withdrawing from the study or the participant being withdrawn from the study by the investigator (AE leading to withdrawal)
- Solicited local or systemic AR lasting beyond 7 days post-injection
- Solicited local or systemic AR that leads to participant withdrawal from vaccine administration
- Solicited local or systemic AR that otherwise meets the definition of an SAE
- Solicited AR with a toxicity score of Grade 3 or greater

An unsolicited AE is any AE reported by the participant that is either not specified as a solicited AR in the protocol or is specified as a solicited AR in the protocol, but starts outside the protocol-defined post-injection period for reporting solicited ARs (ie, for the 7 days after each injection).

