4.6.2 Safety Analyses

Safety and reactogenicity will be assessed by clinical review of all relevant parameters including solicited ARs (local and systemic events), unsolicited AEs, SAEs, MAAEs, AEs leading to discontinuation, safety laboratory test results (Part A only), vital signs, and physical examination findings.

Solicited ARs and unsolicited AEs will be coded by system organ class and preferred term according to the MedDRA for adverse reaction terminology. The Toxicity Grading Scale for Healthy Adult and Adolescent Volunteers Enrolled in Preventive Vaccine Clinical Trials ([DHHS 2007](#)) is used in this study with modification for rash, solicited ARs, and vital signs ([Table 6](#)).

Rash will be graded as:

- Grade 0 = no rash
- Grade 1 = localized without associated symptoms
- Grade 2 = maculopapular rash covering < 50% body surface area
- Grade 3 = urticarial rash covering > 50% body surface area
- Grade 4 = generalized exfoliative, ulcerative, or bullous dermatitis

All safety analyses will be based on the Safety Set, except summaries of solicited ARs which will be based on the Solicited Safety Set. All safety analyses will be provided by age cohort (for Part A and Part B) unless otherwise specified.

The number and percentage of participants with any solicited local AR, with any solicited systemic AR, and with any solicited AR during the 7-day follow-up period after each injection will be summarized. A 2-sided 95% exact CI using the Clopper-Pearson method will be provided for the percentage of participants with any solicited AR.

Number and percentage of participants with unsolicited AEs, SAEs, MAAEs, Grade 3 or higher AEs, and AEs leading to discontinuation from study vaccine or participation in the study will be summarized.

Number of events of solicited ARs, unsolicited AEs/SAEs, and MAAEs will be reported in summarization tables accordingly.

For all other safety parameters, descriptive summary statistics will be provided. [Table 8](#) summarizes the analysis strategy for safety parameters.

Table 8: Analysis Strategy for Safety Parameters

Safety Endpoint	Number and Percentage of Participants, Number of Events	95% CI
Any Solicited AR (overall and by local, systemic)	X	X
Any Unsolicited AE	X	
Any SAE	X	
Any Unsolicited MAAE	X	
Any Unsolicited Treatment-Related AE	X	
Any Treatment-Related SAE	X	
Discontinuation due to AE	X	
Any Grade 3 and above AE	X	
Any Treatment-Related Grade 3 and above AE	X	

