6.3.1.2. TEAEs by System Organ Class and Preferred Term

The following summary tables of TEAEs will be provided by SOC and PT using frequency counts and percentages (ie, number and percentage of subjects with an event):

- All unsolicited TEAEs
- All unsolicited TEAEs that are treatment-related
- All serious TEAEs
- All serious TEAEs that are treatment-related

- All unsolicited TEAEs leading to discontinuation from participation in the study
- All unsolicited Severe TEAEs
- All unsolicited Severe TEAEs that are treatment-related
- All unsolicited TEAEs that are medically-attended

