6.3.1.1. Incidence of Adverse Events

An overall summary of unsolicited TEAEs including the number and percentage of subjects who experience the following will be presented:

- Any unsolicited TEAEs
- Any serious TEAEs
- Any unsolicited TEAEs that are medically-attended
- Any unsolicited TEAEs leading to discontinuation from participation in the study
- Any unsolicited Severe TEAEs
- Any unsolicited TEAEs that are fatal

The table will also include number and percentage of subjects with unsolicited TEAEs that are treatment-related in each of the above categories.

In addition, separate listings containing individual subject adverse event data for unsolicited AEs, unsolicited TEAEs leading to discontinuation from participation in the study, serious AEs, and unsolicited MAAEs will be provided separately.

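### Both SAPs limit the AE-discontinuation summaries to unsolicited events, so a participant who stops because of a solicited reaction can drop out of a summary the protocol promises

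*SAP*

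**What the plan says.** Protocol 4.6.2 commits to the number and percentage of participants with "AEs leading to discontinuation from study vaccine or participation in the study". The matching row of Protocol Table 8 reads "Discontinuation due to AE".

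Protocol 3.4.8.4 lists the circumstances in which a solicited reaction must also be recorded on the AE eCRF. One is a "Solicited local or systemic AR that leads to participant withdrawal from vaccine administration". Another is a solicited reaction that takes the participant out of the study, which the protocol labels in parentheses as an AE leading to withdrawal.

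The Parts A/B SAP, section 6.3.1.1, plans two rows: "Any unsolicited TEAEs leading to discontinuation from study vaccine" and "Any unsolicited TEAEs leading to discontinuation from participation in the study". The two corresponding listings carry the same limit. The one discontinuation table by SOC and PT, in 6.3.1.2, covers "All unsolicited TEAEs leading to discontinuation from participation in the study". The Part C SAP has the same study-participation row, listing and SOC/PT table, and no row for stopping vaccine.

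Section 6.3 of the Parts A/B SAP names events leading to withdrawal from vaccine or study as a safety parameter without the word unsolicited. Section 6.3 of the Part C SAP does so for study withdrawal. Section 7 of the Parts A/B SAP records two changes, both about quantification limits. Section 7 of the Part C SAP declares none. Each SAP states that it prevails where it differs from the protocol.

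**The concern.** The primary safety objective in every part is safety and reactogenicity, and both documents treat all solicited reactions as caused by the injection. Declining a further dose, or leaving, because of such a reaction is a direct measure of tolerability. It is also the case that the planned discontinuation rows exclude.

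The case is foreseeable. Protocol 3.2.5 names vaccine-related generalized urticaria among the possible grounds for withholding further injection. Rash is a solicited systemic reaction, and Grade 3 in Table 6 is a generalized urticarial rash. A participant withheld from the second dose for such a rash starting on Day 3, captured as a solicited reaction, would meet the AE eCRF recording rule and still not enter the vaccine-discontinuation row.

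At stake is a descriptive safety count that could be too low, and an AE table that could disagree with the disposition table without explanation.

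**Working it through.** No figure in the plan is in dispute, so the check is mainly a comparison of text, with arithmetic for scale.

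**Step 1: is a solicited reaction an AE?** Yes. Protocol 3.4.8.1 states: "An AR is any AE for which there is a reasonable possibility that the investigational product caused the AE".

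**Step 2: is it an unsolicited AE?** Not if it starts within the 7-day window. Protocol 3.4.8.1 and 3.4.8.4 reserve that label for events that are not on the solicited list, or are on it but start outside the window.

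**Step 3: does a planned output show it as a discontinuation?**

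| Output | SAP Parts A/B | SAP Part C |
|---|---|---|
| Stopped vaccine, AE summary row (6.3.1.1) | unsolicited only | no row |
| Left study, AE summary row (6.3.1.1) | unsolicited only | unsolicited only |
| SOC/PT table (6.3.1.2) | study participation, unsolicited only | study participation, unsolicited only |
| AE listings (6.3.1.1) | vaccine and study, unsolicited only | study, unsolicited only |
| Solicited-reaction analyses (6.3.2.1) | incidence, grade, day, onset, duration, persistence; no discontinuation | same |
| Disposition (6.2.1) | vaccine and study, with reasons, in table and listing | study in table and listing; vaccine in listing; reasons given |

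Only the last row shows the participant as having stopped, and it is not specified to carry the AE term, grade or relatedness.

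**Step 4: direction.** Restricting the event type can remove participants from the count but cannot add any.

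**Step 5: size in Part A, vaccine row.** Protocol 1.3 gives second injections received as of 05 November 2020: 195, 198 and 194 of 200 for 50 µg, 100 µg and placebo. Missed second doses are therefore 200 − 195 = 5, 200 − 198 = 2 and 200 − 194 = 6. Reasons are not given. The omitted number lies between none and all of these. Intervals are exact Clopper-Pearson: lower limit Beta(0.025; x, n − x + 1), upper limit Beta(0.975; x + 1, n − x).

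| Arm | Least omitted | Most omitted | 95% CI at the most |
|---|---|---|---|
| 50 µg | 0/200 | 5/200 = 2.5% | 0.82 to 5.74% |
| 100 µg | 0/200 | 2/200 = 1.0% | 0.12 to 3.57% |
| Both vaccine arms | 0/400 | (5 + 2)/400 = 1.75% | 0.71 to 3.57% |

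Each omitted participant moves a 200-person arm by 1/200 = 0.5 percentage points and a 20-person Part C arm by 1/20 = 5 points. These ceilings concern second doses only; the documents give no counts from which to bound the study-participation row.

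**The case against.** Several points against the concern have force.

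- **Dose gradient.** A reader might infer that the undercount is worse in the more reactogenic 100 µg arm. The documents do not support this. That arm has the fewest missed second doses (2, against 5 at 50 µg and 6 on placebo), and the placebo count shows that doses are missed for reasons other than vaccine reactogenicity. Pregnancy, COVID-19 and missed visits are all provided for in the protocol. This objection stands.
- **Missing altogether.** A reader might infer that such participants vanish from the report. They do not. Disposition outputs show them with a reason, solicited reactions on the eCRF are listed with maximum grade, and a serious one falls under the serious-TEAE rows, which are not limited to unsolicited events. What is lost is the link between the event and stopping.
- **Table 8.** The missing word unsolicited in its discontinuation row looks decisive but is not. The row for Grade 3 and above is equally unqualified, while the Amendment 3 summary says separate summaries of Grade 3 or higher solicited reactions are not planned. The stronger support is the section 4.6.2 text, read with the recording rule and label in 3.4.8.4. Even that label belongs to a recording rule and is attached only to study withdrawal.
- **Verbally reported reactions.** SAP 6.3.2.1 says these are described as unsolicited, entered on the AE eCRF, flagged as solicited, and added to the solicited evaluation. It does not say whether they also stay in the unsolicited tables, so some may be counted. The omission is clear only for reactions captured in the eDiary.
- **Reach.** Part A reporting is closed, Part B boosters receive one dose, and Part C has a second injection only if it is triggered. For the vaccine row this leaves mainly the Part B participants receiving two doses, whose number is not stated.

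These points limit size and reach. They do not reconcile the SAP tables with the protocol or with the SAPs' own section 6.3.

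**Conclusion.** The inconsistency is real and should be corrected. The protocol promises a summary of AEs leading to discontinuation and has the relevant solicited reactions recorded as AEs. Both SAPs then limit every AE-discontinuation row, SOC/PT table and AE listing to unsolicited TEAEs, without recording a change. Followed as written, the plan can undercount.

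For the Part A vaccine row the undercount is between 0 and 7/400 = 1.75% (95% CI 0.7 to 3.6%) over both vaccine arms, with ceilings of 5/200 at 50 µg and 2/200 at 100 µg. The lower bound of zero is possible: no document shows that such a case occurred. The ceiling assumes that every missed second dose was due to a solicited reaction left out of the unsolicited tables, which is an extreme. No difference in bias between dose groups is shown.

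**What to change.** - In 6.3.1.1 of each SAP, reword the existing discontinuation rows and AE listings to cover any AE, solicited or unsolicited. Take the events from AE eCRF records whatever the answer to the solicited-reaction question, count each participant once, and add a sub-row for solicited reactions.
- In 6.3.1.2 of each SAP, make the same change to the study-participation SOC/PT table. Neither section has a study-vaccine table to change.
- In the Part C SAP, add a study-vaccine row only if the optional second injection is given.
- Apply this to the Part B and Part C outputs, and issue one supplementary table for the completed Part A.

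The cost is revised wording and a changed filter on records that Protocol 3.4.8.4 already requires. This assumes that the AE eCRF links an event to stopping vaccine or study, which the planned unsolicited rows already need. The downside is that reported discontinuation rates may look slightly less favourable.

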6.3.1.2. TEAEs by System Organ Class and Preferred Term

The following summary tables of TEAEs will be provided by SOC and PT using frequency counts and percentages (ie, number and percentage of subjects with an event):

- All unsolicited TEAEs
- All unsolicited TEAEs that are treatment-related
- All serious TEAEs
- All serious TEAEs that are treatment-related

- All unsolicited TEAEs leading to discontinuation from participation in the study
- All unsolicited Severe TEAEs
- All unsolicited Severe TEAEs that are treatment-related
- All unsolicited TEAEs that are medically-attended

6.3.1.3. TEAEs by Preferred Term

A summary table of all unsolicited TEAEs will be provided. PTs will be sorted in a descending order according to the frequency in mRNA-1273 vaccine Total column.

6.3.1.4. TEAEs by System Organ Class, Preferred Term and Severity

The following summary tables of TEAEs will be provided by SOC, PT, and severity (mild, moderate, and severe) using frequency counts and percentages:

- All unsolicited TEAEs
- All unsolicited TEAEs that are treatment-related

6.3.2. Solicited Adverse Reactions

6.3.2.1. Analysis of Reactogenicity

An AR is any AE for which there is a reasonable possibility that the test product caused the AE. The term “Solicited Adverse Reactions” refers to selected signs and symptoms occurring after injection administration during a specified post-injection follow-up period (day of injection and 6 subsequent days).

The solicited ARs are recorded by the subject in eDiary. Any new safety information reported during safety telephone calls or at site visits (including a solicited reaction) that is not already captured in the eDiary will be described in the source documents as a verbally reported event. Any AR reported in this manner must be described as an unsolicited event and therefore entered on the AE eCRF (and marked as “Yes” to the AE eCRF question “Was this a solicited adverse reaction?”), and will be included in the evaluation of solicited ARs in addition to the eDiary data.

The occurrence and intensity of selected signs and symptoms is actively solicited from the participant during a specified post-injection follow-up period (day of injection and 6 subsequent days), using a pre-defined checklist (ie, solicited ARs).

The following local ARs will be solicited: pain at injection site, erythema (redness) at injection site, swelling (hardness) at injection site, and localized axillary swelling or tenderness ipsilateral to the injection arm.

The following systemic ARs will be solicited: headache, fatigue, myalgia (muscle aches all over the body), arthralgia (aching in several joints), nausea/vomiting, rash, fever, and chills.

The solicited ARs will be graded based on the grading scales presented in Table 6 in the protocol, modified from the Toxicity Grading Scale for Healthy Adult and Adolescent Volunteers Enrolled in Preventative Vaccine Clinical Trials (DHHS 2007). Investigator will assess the Grading for rash and Grade 4 events (with exception of fever).

If a solicited local or systemic AR continues beyond 7 days post injection, the participant will be prompted to capture solicited local or systemic AR in the eDiary until resolution.

All solicited ARs (local and systemic) will be considered causally related to injection.

All solicited ARs analyses will be based on the Solicited Safety Set. All solicited ARs analyses will be provided by age cohort and vaccination group as defined in [Section 6.1](#) for each injection (first or second) (Part A only) and any injection (Part A and Part B separately), unless otherwise specified.

The number and percentage of subjects who reported each individual solicited local AR (has a severity grade of Grade 1 or greater) and solicited systemic AR (has a severity grade of Grade 1 or greater) during the 7-day follow-up period after each injection will be tabulated by age cohort, vaccination group, severity grade, and injection. The number and percentage of subjects who reported each individual solicited AR will also be summarized by age cohort, vaccination group, severity grade, day of reporting and injection. The number and percentage of subjects experiencing fever (a temperature greater than or equal to 38.0°C/100.4°F by the oral, axillary, or tympanic route) by severity grade will be provided.

A two-sided 95% exact confidence interval (CI) using the Clopper-Pearson method will be provided for the percentage of subjects who reported any solicited local AR, solicited systemic AR, or any solicited AR.

The onset of individual solicited AR is defined as the time point after each injection at which the respective solicited AR first occurred. The number and percentage of subjects with onset of individual solicited AR will be summary by age cohort, vaccination group, study day relative to the corresponding injection (Day 1 through Day 7), and injection.

The number of days reporting each solicited AR will be summarized descriptively and for the following time windows (1-2 days, 3-4 days, 5-6 days, and ≥ 7 days) by age cohort, vaccination group, and injection. The number of days will be calculated as the days of the solicited AR is reported within the 7 days of injection including the day of injection, no matter it is intermittent or continued. If the solicited AR continues beyond 7 days, the consecutive days a solicited AR is reported after 7 days will be included (eg, an event that lasted 5 days in the first 7 days post injection and 3 consecutive days beyond 7 days post injection, the duration will be reported as 8 (5+3) days.)

The number and percentage of subjects who reported solicited rash and lymphadenopathy assessed by healthcare provider will be summarized by age cohort, vaccination group, severity grade, and injection.

Solicited ARs collected on eDiary and those collected on AE aCRF will be provided in a listing, and the maximum grade from eDiary and AE aCRF will be presented. All solicited ARs (including rash) that continue beyond 7 days post injection will be presented in separate data listings.

